### **Aim 3. Examine feasibility of the optimal intervention (identified in Aim 2) with a pilot study (n = 90) in the safety-net clinics.**

**Analysis Plan for Aim 3:** We will obtain information on the following outcomes that will be important for developing a subsequent efficacy randomized controlled trial (RCT).

**Enrollment rates.** We will assess whether enrollment rates are similar across the clinic sites.

**Sufficient time for intervention procedures.** Because clinic sites may differ in their patient flow and visit wait times, we will track the number of participants who complete the tablet-based procedure within the time constraints allowed by the clinic and determine whether time allotted for completing the intervention is similar and sufficient across all sites. We expect an 85-90% completion rate to determine feasibility.

**Potential for contamination.** We will determine the appropriate level of randomization (patient, provider, or clinic) and the degree to which contamination occurs at each level. We will use visit history data in the EMR to examine the percentage of patients who visit more than one clinic and see more than one provider. For example, if there is significant crossover of patients to different providers at the same clinic, then we will randomize at the clinic-level in the subsequent efficacy trial.

**Intermediate outcome – active parent participation.** We hypothesize that exposure to the self-persuasion intervention will positively influence active parent participation in discussions with providers. We will apply [name]'s scheme to code the 3 types of active communication (Aim 1b). To estimate effect sizes for the subsequent efficacy RCT, we will compute means, standard deviations, and ranges of parent and provider communications and compare them to data collected in Aim 1b. We will use multivariable mixed linear regression modeling to explore factors associated with parent degree of participation (e.g., English vs. Spanish language). This method models the provider as a random effect to adjust for potential clustering of patients by provider; parent/patient characteristics of interest will be modeled as fixed effects.

**Primary, quantitative outcomes – HPV vaccine uptake:** We hypothesize that exposure to the self-persuasion intervention will increase 1-dose and 3-dose HPV vaccine coverage rates. We will use the EMR to measure vaccine uptake. These data will help estimate effect sizes of the self-persuasion intervention, compared to the information-only group, guiding the design and sample size for the subsequent efficacy RCT. We will also measure HPV vaccine-specific measures of intentions, benefits, and barriers .

**After completing Stage 3,** we will have quantitative and qualitative data to determine whether our self-persuasion intervention is feasible and acceptable across clinics – data that will guide us in refining intervention and measurement procedures. Thus, at the end of this stage, we will have a well-characterized and feasible intervention promoting HPV vaccination ready to be tested in future efficacy trial.

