### In addition to their adolescents receiving usual care, all parents in this study will be:

- a) Mailed an invitation letter describing the study;
- b) Called to verbally describe study, invite to participate, and confirm willingness to come to an in-person meeting; and
- c) Asked to complete a baseline survey during/after the recruitment call, except for Stage 3, when parents will not complete the baseline survey and will be approached in-person instead of by phone to obtain consent and verify eligibility

**Parents enrolled in Aim1a will be** asked to generate pro-vaccine arguments after using a tablet-based application that provides HPV vaccine information suited for parents of adolescent females & males.

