### **Additional Procedures for Each Stage**

**Stage 1:** To accomplish Aim 1a, we will recruit 42 parents of unvaccinated adolescents and 11 parents of adolescents who *have* started the series to gather the full range of arguments for HPV vaccination (n=53, stratified by sex). During a 1-hour study session, a bilingual RA will obtain informed consent and show the parent how to use a tablet-based application. A short video will provide HPV vaccine information suited for parents of adolescent females and males. Then the RA will use a series of questions to prompt parents to verbalize as many pro-vaccine arguments as they can. Afterward, the RA will use a cognitive interviewing-based guide to probe about the self-generated arguments. Parents will then be asked to listen to, rate, and choose among *peer-generated* arguments. The RA will ask questions to clarify whether peer-generated arguments are clear and understood. Finally, participants will be given the entire set of arguments. We will use probes to determine whether they can distinguish among and select their preferred arguments.

To accomplish Aim 1b, we will identify parents of unvaccinated adolescents with upcoming appointments at the 3 neighborhood and 3 school clinics that see the most adolescents. At least 5 parent-child dyads per provider will be recruited (n=53). We will only record discussions between parents and providers who are language concordant. Audiorecording equipment will be set up in the clinic room; research staff will not be present during discussions. After the participant meets with the provider and is discharged, the RA will conduct a 10-minute interview. Parents will be asked open-ended questions about their prior experience with this provider and whether the HPV vaccine was discussed during the visit. Then, we will administer a survey about provider recommendation, HPV vaccine benefits and barriers, and perceived involvement in medical care.

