**Stage 2:** To accomplish Aim 2, we will randomly assign 168 undecided parents (of 84 girls & 84 boys) to 1 of 4 intervention conditions that differ by levels of cognitive processing and choice. In a 1-hour study session, parents will use a tablet-based application that directs them to either: verbalize their own arguments based on topics they choose (deep processing, high choice), verbalize arguments based on topics assigned to them (deep processing, low choice), listen to arguments based on topics they choose (shallow processing, high choice), or listen to arguments based on topics assigned to them (shallow processing, low choice). We will conduct exit interviews to assess parents' perspective on the tablet application, self-persuasion condition, and how their beliefs and experiences shape feelings about the HPV vaccine. Adolescents who accompany their parent to the study appointment at their Parkland clinic will have the opportunity to receive the 1st HPV vaccine dose from a Parkland nurse immediately after the exit interview. We will synthesize quantitative and qualitative data to select the optimal intervention condition for that will be used in Stage 3.

**Stage 3:** To accomplish Aim 3, we will recruit from pediatric neighborhood and school-based clinics, with a target of 15 parents per site (n=95). Parents will be randomly assigned to either: 1) self-persuasion plus information (optimal intervention condition from Aim 2; n=48), or 2) HPV information only (n=47). For the self-persuasion group, we will follow procedures in Stage 1. Parents in the information only group will be given a tablet and instructed to listen to information about HPV infections and the benefits and risks of the HPV vaccine. We will audiorecord the parent-provider discussion. Immediately after the visit, an RA will conduct an exit interview in which participants will be asked questions about their experiences using the tablet and their communication with the provider.

We expect to review the medical records of 369 adolescents whose parents were enrolled in our study. Medical records will be reviewed after 12 months for HPV vaccine dates. We will also abstract info for 3 other vaccines (TDAP, MCV4, & influenza) that are correlated with HPV vaccination.

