Coders will co-code 5 recordings to establish rating agreement, and will code 3 more recordings semi-independently engaging in discussion to resolve differences. To evaluate inter-coder reliability, we will use Krippendorf’s alpha, a measure of agreement that allows for the analysis of categorical and continuous variables in the presence of missing data. To describe the communicative environment, we will compute means, standard deviations, and ranges of parent and provider communications. To explore the effect of provider discussions, we will compare parents’ responses to baseline and exit survey items regarding vaccine benefits and barriers (decisional balance), and post-visit perceived involvement in care.

**Qualitative Data Analysis.** Interviews will be audiotaped and transcribed. Drs. [name], [name], and [name] will perform in-depth analysis of all transcripts using NVivo 9.0 (QSR International). Data will be analyzed within and across transcripts. Through iterative coding and interpretation, the team will code actual utterances, expressions and concepts against participant characteristics to identify themes and relationships. We will organize these codes into a codebook that relates data to behavioral theory. Regular meetings will enable the team to test emergent themes and interpretation against the knowledge base of experts in pediatrics (e.g. [name], [name]), self-persuasion ([name]), vaccination ([name]), and intervention development ([name]).

**At the end of Stage 1, we will know:** (1) the range of pro-vaccine arguments underserved parents generate, (2) which arguments are easiest to generate, most prevalent, and persuasive, and (3) range and degree to which parents participated in HPV vaccine discussions. We will also know which peer-generated arguments are rated as clear, comprehensible, and distinct from other arguments. With these data, we will select the most prevalent argument topics with easy-to-generate arguments for the self-persuasion intervention conditions in Aim 2. Baseline descriptive information about the communicative environment will be compared with parent-provider discussions after exposure to the optimal self-persuasion intervention in Aim 3.

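### The participation effect size in Aim 3 is to be taken against the earlier, non-randomised Aim 1b cohort, and no contrast between the two randomised arms is specified for it

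*Combined protocol and SAP*

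**What the plan says.** Under the intermediate outcome in the Analysis Plan for Aim 3, the protocol hypothesises that "exposure to the self-persuasion intervention will positively influence active parent participation in discussions with providers". Its effect sizes are meant for the later efficacy trial, and the method is: "we will compute means, standard deviations, and ranges of parent and provider communications and compare them to data collected in Aim 1b". The summary of what will be known at the end of Stage 1 announces the same comparison: "Baseline descriptive information about the communicative environment will be compared with parent-provider discussions after exposure to the optimal self-persuasion intervention in Aim 3".

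A mixed linear model follows, with provider as a random effect and parent or patient characteristics as fixed effects. Its stated purpose is to "explore factors associated with parent degree of participation (e.g., English vs. Spanish language" and similar). Randomised arm is not named.

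Stage 3 is nevertheless a randomised comparison: "Parents will be randomly assigned to either: 1) self-persuasion plus information (optimal intervention condition from Aim 2; n=48), or 2) HPV information only (n=47"). The recording of discussions is stated after both arms are described and is not limited to one of them. For vaccine uptake, the same analysis plan does use the randomised comparator, seeking "effect sizes of the self-persuasion intervention, compared to the information-only group, guiding the design and sample size for the subsequent efficacy RCT".

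**The concern.** The hypothesis concerns self-persuasion. The comparison written for it cannot isolate self-persuasion, for two reasons.

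First, both Stage 3 arms receive HPV information on a tablet, while the Aim 1b procedures list no tablet step. Even with a perfectly comparable Aim 1b cohort, the contrast would be self-persuasion plus information against neither.

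Second, the cohorts differ in ways that randomisation does not control. Aim 1b is an earlier stage, recruited by phone, with a baseline survey. These features apply to all parents "except for Stage 3, when parents will not complete the baseline survey and will be approached in-person instead of by phone". For Aim 1b the protocol also says "We will only record discussions between parents and providers who are language concordant". No such limit is stated for Stage 3, and the plan itself gives language as an example of a factor associated with participation.

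It is also not explicit which Stage 3 parents enter the comparison. The Aim 3 text does not separate the arms, whereas the Stage 1 summary refers to discussions after self-persuasion.

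At stake is a planning estimate for the efficacy trial that could be too large or too small for reasons unrelated to self-persuasion, when the data for a randomised estimate are already to be collected.

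**Working it through.** The documents give no SD, effect size or power for participation, so there is no stated figure to reproduce. The counts agree: 48 + 47 = 95, and 53 + 53 + 168 + 95 = 369.

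**Inputs from the documents.** Self-persuasion arm 48, information-only arm 47 (Additional Procedures for Each Stage, Stage 3); Aim 1b cohort 53 (same section, Stage 1); at least 5 dyads per provider in Aim 1b; 18 providers expected across Aims 1b and 3 (Study Procedures).

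**Assumptions.** Outcome SD = 1; provider intraclass correlation (ICC) 0.05 to 0.10; 10 providers in Aim 1b, the most that 53 dyads at 5 or more each allow; 8 in Stage 3 if none are shared (18 - 10), or 8 to 18 if some are.

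**Step 1: precision without clustering.** 95% half-width = 1.96 × √(1/n₁ + 1/n₂).

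| Contrast | n | Half-width (SD) |
|---|---|---|
| Self-persuasion vs information only (randomised) | 48 vs 47 | 1.96 × √0.0421 = 0.402 |
| Self-persuasion vs Aim 1b | 48 vs 53 | 1.96 × √0.0397 = 0.391 |
| Both Stage 3 arms pooled vs Aim 1b | 95 vs 53 | 1.96 × √0.0294 = 0.336 |

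**Step 2: precision with provider clustering.** Total SD is held at 1.

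- *Randomised contrast.* Parents are randomised individually, so providers can see both arms and much of the provider effect cancels. With perfect balance within provider the half-width is 0.402 × √(1 - ICC): 0.392 at ICC 0.05 and 0.382 at 0.10. Generalised least squares with chance imbalance gives 0.398 to 0.400 and 0.390 to 0.395.
- *Aim 1b contrast, no shared providers.* With equal numbers per provider, variance = ICC/8 + (1 - ICC)/48 + ICC/10 + (1 - ICC)/53. At ICC 0.05 this is 0.0260 + 0.0229 = 0.0490, half-width 0.434. At ICC 0.10 it is 0.0313 + 0.0270 = 0.0582, half-width 0.473.
- *Aim 1b contrast, shared providers.* Generalised least squares gives about 0.38 to 0.39.

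The randomised contrast is therefore about as precise as the Aim 1b contrast, or more precise if the stages share no providers.

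**Step 3: what each contrast estimates.** Let s be the effect of self-persuasion over information only, and b the sum of the information effect and all cohort differences.

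- Randomised contrast: s
- Self-persuasion vs Aim 1b: s + b
- Pooled Stage 3 vs Aim 1b: (48/95)s + b = 0.505s + b

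The documents give no basis for b. As a purely hypothetical range, take s = 0.3 SD and b from -0.3 to +0.3 SD:

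- Self-persuasion vs Aim 1b: 0.3 - 0.3 = 0.0 to 0.3 + 0.3 = 0.6 SD
- Pooled: 0.15 - 0.3 = -0.15 to 0.15 + 0.3 = 0.45 SD
- Randomised: 0.3 SD throughout, provided there is no carry-over between arms

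No observed value of s + b allows s to be recovered.

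**The case against.** The strongest reply is that the participation hypothesis names no comparator and that the Stage 3 arm is self-persuasion plus information. Comparing that package with ordinary recorded visits would then be a legitimate, if biased, question. But the uptake hypothesis is worded much the same way and is paired with the information-only group. The package reading is possible, but the plan does not state it.

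Other points have partial force:

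- **Pooling.** The Stage 1 summary points to the self-persuasion arm, so pooling is the less natural reading. The pooled figures matter only if the Aim 3 text is taken literally.
- **Open factor list.** The model's factors are given only as examples, so arm could be added. Its fixed effects are described as parent or patient characteristics, however, and a hypothesised effect should not depend on inference.
- **Carry-over.** One provider may see both arms, and the plan treats contamination as an open question. The randomised contrast could be affected; Aim 1b precedes the intervention and is free of this. This is a real limitation, but it does not make Aim 1b the better estimate of self-persuasion.
- **Sample sizes.** The protocol plans to analyse mothers only and elsewhere gives 90 for the pilot and 50 recorded discussions. With an assumed 45 per arm, the half-widths become 0.41 SD (45 vs 45) and 0.40 SD (45 vs 50), so the comparison is unchanged.
- **Cohort differences.** The language limit is unstated for Stage 3, which is weaker than a documented difference. Eligibility and clinics may also differ, but the documents are inconsistent: the procedures drop the question on indecision for Aim 3, while Table 3 lists it without exception. The case does not rest on these.
- **Importance.** This is an intermediate outcome in a pilot, and the sample size of the later trial is tied to uptake. That limits the harm, but the Aim 3 text still intends these effect sizes for that trial.

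**Conclusion.** The concern holds. Followed as written, the plan yields a non-randomised participation estimate that cannot separate self-persuasion from tablet information or cohort differences. This follows from which comparison is specified and does not depend on any assumed number. The size and direction of the bias cannot be derived from the documents; the 0.0 to 0.6 SD range is illustrative only.

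The randomised alternative costs essentially no precision: 0.40 against 0.39 SD unclustered, and 0.38 to 0.40 SD with an assumed ICC of 0.05 to 0.10. The figures of about 0.43 to 0.47 SD for Aim 1b without shared providers rest on the assumed provider counts.

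The point should be fixed, but its reach is limited to an intermediate outcome. The uptake analysis stands.

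**What to change.** In the Analysis Plan for Aim 3, name the self-persuasion minus information-only difference within Stage 3 as the effect size for active parent participation. Estimate it by adding randomised arm as a fixed effect to the planned mixed model with provider random effect, and report it with a 95% confidence interval. Keep the Aim 1b comparison as descriptive context, shown separately for each Stage 3 arm. If a contrast with visits without a tablet is also wanted, state it as a separate, non-randomised estimate. Note possible carry-over through shared providers when interpreting the result.

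The cost is analysis-plan wording only, since the recordings, coding and model are already planned. The drawback is that an interval of about ±0.40 SD leaves the planning estimate imprecise.
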